## Types of Sampling

For selecting the type of sample, the type of design must be considered, which in this case is experimental. Therefore, the appropriate approach is probabilistic sampling. According to Ñaupas Paitán et al. (2018), this is based on the law of large numbers and probability calculations (Ander-Egg, 1995). From these two laws, those related to the sampling procedure are derived. These are: Law of statistical regularity. This implies that the units of a sample (n) have the same characteristics as the population (N) to which they belong. Law of inertia of large numbers. According to this law, the result obtained in a sample (n) is almost always the same as that found in the population (N). Based on this law, it is possible to generalize the results. Law of permanence of small numbers. This law states that if two samples are obtained from a population (N), in each of the samples (n) there will be a small number of units that have the peculiar characteristics of the population, in the same proportion.

In this way, probability samples have many advantages, perhaps the main one being that the size of the error in our predictions can be measured. It is even said that the main objective in the design of a probability sample is to minimize this error, which is called the standard error (Kish, 1995; Kalton and Heeringa, 2003). Probability samples are essential in cross-sectional research designs, both descriptive and correlational-causal (opinion polls or surveys, for example), where the aim is to estimate variables in the population. These variables are measured and analyzed

with statistical tests in a sample, where it is assumed that the sample is probabilistic and that all elements of the population have the same probability of being selected. The sample units or elements will have values very similar to those of the population, so that the measurements in the subset will give us accurate estimates of the larger set. The accuracy of these estimates depends on the sampling error, which can be calculated.

### **Sample Size Calculation**

The sample size was calculated using EPIDAT version 4.2 for independent samples, considering a 95% confidence level ( $\alpha = 0.05$ ) and 80% statistical power ( $\beta = 0.20$ ). A standard deviation of 60 seconds was used, taken from previous studies of 5 km races in a similar population (Cruz et al., 2022), and a minimum clinically relevant difference of 60 seconds in race time between the groups was established. Under these assumptions, an approximate sample size of 8 participants per group was estimated; however, to strengthen the validity of the study and anticipate possible losses during follow-up, it was decided to include 10 participants per group, for a total of 20 participants.

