## **Study Assumptions**

### **Primary Alternative Hypothesis**

The polarized TID model is superior by at least 60 seconds in 5k running time, compared to the threshold TID in a 12-week program in recreational distance runners.

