### **Primary Null Hypothesis**

No differences in 5k running time were identified between the polarized TID model compared to the threshold TID model in a 12-week program in recreational distance runners.

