## Inclusion and Exclusion Criteria

**Table 4.** *Inclusion and exclusion criteria*

Inclusion	Exclusion

 
• Age between 20 and 45 years
 
• 1 to 3 years of experience
 
• Men's race time between 25:00 and 40:00
 
• Women's race times between 28:00 and 43:00
 
• Residing in Bogotá or surrounding municipalities at an altitude of 2,640 meters above sea level
 
• Have a GPS system
 
	
 
• Having a chronic non-communicable disease
 
• Smokers or drinkers
 
• Having some musculoskeletal injury.
 
• DO NOT sign the informed consent form
 
• 10% compliance with training sessions.
 

Source: own elaboration.

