## Tests

### 5000 Meter Flat Test (5km)

The 5000-meter (5K) race will be used as a means of analyzing the race time variable. Rosa-Guillamón & García-Cantó (2022) state that this race consists of covering 5000 meters, or 12.5 laps, of official outdoor athletics track at the highest possible speed. This athletic event is the shortest distance among those classified as "endurance" or long-distance races, whose main characteristic is the predominance of aerobic energy metabolism, expressed through aerobic capacity and power as a function of time and intensity of the effort. The test-retest reliability of track running tests has demonstrated high consistency coefficients, with intraclass correlation coefficient (ICC) values exceeding 0.90 reported when environmental variables such as surface, weather conditions, time of day, and warm-up standardization are adequately controlled. This level of reproducibility indicates low within-subject variability and a reduced standard error of measurement, supporting its use in intervention studies and monitoring of aerobic performance. Methodologically, Hopkins (2000) establishes statistical criteria for interpreting reliability in sports science, while Atkinson and Nevill (1998) describe procedures for quantifying measurement error and ensuring consistency in physical tests applied in a sports context—foundations that support the use of the 5000-meter test as a reliable instrument in research with adults.

A review of the literature revealed no studies using the 5-kilometer test with recreational runners in Colombia, and therefore no reference values were found. Consequently, the application of this test will serve as a reference for other studies related to recreational runners.

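### The 60 s SD behind the sample size is hard to reconcile with the 15-minute eligibility windows, and even at 60 s, 8 or 10 runners per group do not give 80% power

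*Protocol*

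**What the plan says.** The Sample Size Calculation section uses a formula for independent samples, "considering a 95% confidence level" (alpha 0.05) and "80% statistical power". The difference sought is 60 s in race time between the groups. On variability it says "A standard deviation of 60 seconds was used" and gives earlier 5 km race studies as the source. The result is about 8 per group, raised to 10 per group (20 in total) partly to allow for losses. No pre-post correlation or covariate is mentioned.

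The Primary Alternative Hypothesis reads "The polarized TID model is superior by at least 60 seconds in 5k running time". The Primary Null Hypothesis is a plain absence of difference in running time. Sidedness is not stated.

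Table 4 (Inclusion and Exclusion Criteria) admits "Men's race time between 25:00 and 40:00" and "Women's race times between 28:00 and 43:00".

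The Specific Objectives speak of evaluating changes in 5 km time between the groups, and Table 6 has columns for each runner's initial and final time. The section on the 5000 m test cites "intraclass correlation coefficient (ICC) values exceeding 0.90" for track running tests under controlled conditions. It also says that no reference values were found for recreational runners in Colombia.

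**The concern.** An SD taken from 5 km races reads as the spread of race times between people. A value of 60 s implies a far more uniform group than Table 4 would admit. If the true spread is larger, a 60 s training effect is small beside the differences between runners. A chance baseline gap between two arms of 10 could then be as large as the effect sought.

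The stated sample size also has to follow from its own inputs, whatever the right SD is. If it does not, the trial's only power statement is unsupported, and a null result would say little about whether a 60 s difference exists.

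**Working it through.** **1. The plan's own figure.** Inputs from the Sample Size Calculation: difference 60 s, SD 60 s, alpha 0.05, power 80%, two independent groups.

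- Normal formula: n per group = 2 × (1.960 + 0.842)² × (60/60)² = 2 × 7.85 = 15.7, so 16. The noncentral t distribution gives 17.
- One-sided: 13 by the normal formula, 14 by noncentral t.
- Neither gives 8. The one-sample or paired formula, (1.960 + 0.842)² × (60/60)² = 7.85, rounds up to 8, and 8 is also half of 16. The documents do not show which route, if either, was taken.
- Power by noncentral t, SD 60 s: 10 per group gives 56% two-sided (69% one-sided); 8 per group gives 46% (60% one-sided).

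**2. 60 s against Table 4.**

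- Under a normal distribution, about 95% of times lie within 2 × 1.96 × 60 = 235 s. Each window is 40:00 − 25:00 (or 43:00 − 28:00) = 900 s, so 235 s is about a quarter of it.
- The women's window is shifted by 180 s. In a 50:50 mix, a shift of that size alone adds an SD of 90 s. With 60 s within each sex, the pooled SD is √(60² + 90²) = 108 s.
- A sample filling one window would have an SD of 900/6 = 150 s, 900/4 = 225 s, or 900/√12 = 260 s (uniform). These values are assumptions, because the documents give no SD for this population.

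**3. Power for 60 s, 10 per group, two-sided 0.05, final times compared without baseline.**

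| Assumed SD of race time | Power |
|---|---|
| 60 s | 56% |
| 108 s | 22% |
| 150 s | 13.5% |
| 225 s | 8.7% |
| 260 s | 7.8% |

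**4. Chance imbalance at baseline.** The standard error of the difference between arms is SD × √(2/10): 67 s at SD 150 s and 116 s at SD 260 s. A baseline gap of 60 s or more in either direction would occur by chance in about 37% and 61% of randomisations.

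**5. 60 s as an SD of change.** Change SD = SD × √(2(1 − r)), where r is the pre-post correlation.

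- r = 0.90: 67 s (SD 150 s) to 116 s (SD 260 s).
- r = 0.95: 47 s to 82 s.
- A change SD of exactly 60 s needs r of about 0.92 (SD 150 s) to 0.97 (SD 260 s).

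**6. Power with baseline time as a covariate.** Residual SD = SD × √(1 − r²); 10 per group, 17 degrees of freedom.

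| Race-time SD | r | Residual SD | Power |
|---|---|---|---|
| 150 s | 0.90 | 65 s | 49% |
| 150 s | 0.95 | 47 s | 77% |
| 260 s | 0.90 | 113 s | 20% |
| 260 s | 0.95 | 81 s | 35% |

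At r = 0.90 the variance falls by a factor of 1/(1 − 0.81) = 5.3. A power of 80% needs a residual SD of about 45 s, which means r of about √(1 − (45/150)²) = 0.95 at SD 150 s and √(1 − (45/260)²) = 0.98 at SD 260 s. Adding sex (16 degrees of freedom) changes these powers by less than one percentage point.

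**The case against.** Four points on the other side deserve an answer.

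- **Eligibility limits are not an observed spread.** This stands. A reader might infer that 60 s is impossible and that power is 8% to 14%. The documents do not support either statement: the recruits could cluster inside the windows, and 8% to 14% belongs to an assumed SD of 150 to 260 s. With an SD of 108 s, power is about 22%.
- **The protocol does not say that baseline will be ignored.** This also stands. A reader might infer from the hypotheses and the independent-samples formula that baseline time has no role in the comparison. The Specific Objectives speak of changes, both times are recorded, and the model may be set out in a statistical analysis plan that is not at hand. The missing model is therefore not the error. The error lies in the sample-size statement, which the protocol does make.
- **60 s could be an SD of change.** It could. The protocol cites reliability above 0.90, so 0.90 is a floor and the 67 to 116 s it implies are upper values under that input; at 0.95 the range of 47 to 82 s includes 60 s. A test-retest coefficient is not a 12-week correlation across a training programme, however, and the latter is not given. The section also does not describe 60 s as an SD of change. Even so read, 10 per group gives about 56%.
- **ANCOVA does not rescue the design.** Correct. A reader might infer that baseline adjustment restores 80%, but at a correlation of 0.90 and race-time SDs of 150 to 260 s it gives 49% to 20%.

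**Conclusion.** The point holds in two parts of different strength.

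The first needs no outside assumption. Eight per group at 80% power does not follow from the stated inputs under an independent-samples calculation. About 17 per group are needed two-sided, or about 14 one-sided, and the planned 10 give about 56% two-sided.

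The second rests on judgement. As a spread of race times, which is how the text presents it, 60 s is not credible beside two 900 s windows offset by 180 s. The loss of power depends on an SD that the documents do not supply: about 22% at 108 s, and about 14% to 8% at 150 to 260 s, for an unadjusted comparison of final times. None of these values is near 80%.

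Using the baseline time already collected is the cheapest gain in precision and allows for chance imbalance between small arms. Whether it is enough depends on a 12-week correlation that is not stated.

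**What to change.** In the Sample Size Calculation:

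- State whether 60 s is the SD of race time, of change, or of the residual after baseline adjustment. Make it compatible with Table 4, and give the pre-post correlation assumed.
- State whether the test is one- or two-sided, and correct the 8 per group with an independent-groups formula.
- Restate the power of 10 per group over a range of residual SDs, for example 45, 65 and 115 s, which give about 80%, 49% and 20% for a 60 s difference.

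State the primary comparison as ANCOVA of final 5 km time on arm, baseline 5 km time and sex, reporting the adjusted difference in seconds with its 95% CI. If a statistical analysis plan already says this, a reference to it is enough.

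The cost is wording plus one or two degrees of freedom; no additional measurement is needed. If the residual SD cannot be argued to be about 45 s, the protocol should either plan more runners or say plainly that power for 60 s is below 80%.

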## **Type of Research**

Two-arm parallel randomized controlled clinical trial (RCT) designed with the CERT and CONSORT guidelines, Friedman, Furberg, DeMets, Reboussin and Granger (2015).

Furthermore, in relation to the research approach and in accordance with the objectives and variables to be investigated, the design type is experimental, as stated by Ñaupas Paitán et al. (2018). Experimental design allows for establishing the consequences achieved after applying an experiment. In this method, the researcher controls the independent variable, which is generally a treatment, applies it to the dependent variable, and explains what has happened.

Experiments manipulate treatments, stimuli, influences, or interventions (called independent variables) to observe their effects on other variables (dependent variables) in a controlled situation. In other words, experimental designs are used when the researcher intends to establish the possible effect of a manipulated cause.

In this research, the aim is to determine the effects of polarized, and threshold DIE intensity distribution models on running time in recreational runners between 20 and 45 years old.

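### Eight per group does not follow from the protocol's own inputs: they require 16 to 17 per group, and the planned 10 per group gives about 56% power, not 80%

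*Protocol*

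**What the plan says.** The Sample Size Calculation section of the protocol describes a calculation in EPIDAT 4.2 "for independent samples, considering a 95% confidence level" (alpha 0.05), with 80% power. The SD is 60 s, taken from a published study of 5 km races, and the smallest relevant difference in race time between the groups is 60 s. The result is "an approximate sample size of 8 participants per group was estimated". To strengthen validity and allow for losses, "it was decided to include 10 participants per group, for a total of 20 participants".

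The Type of Research section confirms a two-arm parallel randomised design. The section does not say whether the test is one- or two-sided. It gives no pre-post correlation, baseline adjustment or dropout rate, and does not say whether 60 s is the SD of final times, of changes or of residuals. The primary null is worded as no difference ("No differences in 5k running time were identified between the polarized TID model compared to the threshold TID model"). The primary alternative is directional: "The polarized TID model is superior by at least 60 seconds in 5k running time".

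**The concern.** The difference equals the SD, so the standardised difference is 1.0. At that effect size a two-group comparison with 80% power needs about 16 or 17 per group, a figure easily recognised. Eight is half of it, a gap too large for rounding or for the word approximate to cover.

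This calculation is the only justification given for enrolling 20 people, and it concerns the primary comparison. A reader who believes the trial has 80% power may take a non-significant result as evidence that the two training models perform alike. In fact the chance of missing the protocol's own target difference would be roughly double the 20% that the protocol states.

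**Working it through.** **Inputs**, all from the Sample Size Calculation section: two independent groups of equal size; alpha 0.05; power 0.80; SD 60 s; difference 60 s; so d = 60/60 = 1.0. Two-sided testing is my assumption, based on the 95% confidence level and the no-difference null. One-sided results are shown as well.

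**1. Can the stated 8 be reproduced?**

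- Two independent means, two-sided, normal approximation: n per group = 2 × (1.960 + 0.842)² / d² = 2 × 7.85 = 15.70, so **16**.
- The same with the t distribution: 16.71, so **17** (power is 78.1% at 16 and 80.7% at 17).
- One-sided, normal: 2 × (1.645 + 0.842)² = 12.37, so **13**.
- One-sided, t: 13.10, so **14**.

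No two-group version gives 8. Without the factor 2, the two-sided normal formula gives (1.960 + 0.842)² = 7.85, which rounds up to exactly 8. That is the formula for a single sample or for paired differences.

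**2. Power for a 60 s difference at the planned size**

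| Per group | Two-sided t | Two-sided normal | One-sided t | One-sided normal |
|---|---|---|---|---|
| 8 | 46.1% | 51.6% | 60.1% | 63.9% |
| 10 | 56.2% | 60.9% | 69.4% | 72.3% |

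No cell reaches 80%.

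**3. What 10 per group can show (two-sided t)**

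- Difference detectable with 80% power: d = 1.325, so 1.325 × 60 = 79.5 s. With 8 per group, d = 1.507, so 90.4 s.
- Expected half-width of the 95% confidence interval at 10 per group: 2.101 × 60 × √(2/10) = 2.101 × 26.83 = 56 s, nearly the whole target difference.

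**4. What would make the planned size sufficient?**

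- For 80% power at 10 per group, the SD of the analysed quantity must be at most 60 / 1.325 = 45.3 s.
- For 80% power at 8 per group, it must be at most about 40 s (t) to 43 s (normal).
- If 60 s is the SD of race times at one time point, then by the normal approximation 8 per group would need a pre-post correlation of about 0.71 with baseline adjustment (ANCOVA), or 0.75 with change scores. The protocol states no correlation.

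**The case against.** The strongest defence is that runners are measured before and after. An analysis using the baseline could have a residual SD well below 60 s, and 10 per group could then be adequate. With a correlation of 0.7, for example, baseline adjustment gives a residual SD of 60 × √(1 − 0.49) = 42.8 s and about 84% power at 10 per group. That is a sound route to a valid claim, but it is not the one taken. The stated calculation is for independent samples with an SD of 60 s, and it gives no correlation or residual SD. The Specific Objectives speak of evaluating changes without naming an adjusted analysis.

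Three further points deserve credit:

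- **Cause.** The protocol names software, not a formula, so the missing factor 2 is an inference. Reading a result of 16 per group as the trial total would also give 8, as would a one-sided paired t-test (7.73). None of these is a valid two-group calculation, so the error stands whichever slip produced it.
- **Sidedness and method.** The directional alternative might suggest a one-sided test. The chance of missing 60 s at 10 per group would then be about 28% to 31%, rather than 39% to 44%. Power remains below 80% either way.
- **Meaning of the SD.** The inclusion criteria admit a 15-minute (900 s) range of race times within each sex. If 60 s is meant as the spread of final times, it looks small against that range. With an assumed SD of 150 to 260 s, unadjusted two-sided power at 10 per group would be only about 14% down to 8%. This does not excuse the arithmetic, but it means the 56% depends on taking the 60 s at face value.

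**Conclusion.** The concern holds. On the protocol's own inputs, 8 per group is about half of what a two-sided two-group comparison requires (16 by the normal approximation, 17 by the t-test), and it is also too few for a one-sided test. At 10 per group the power is 56% (two-sided t-test), falling to 46% if 8 per group complete. The most favourable reading, one-sided with the normal approximation and no losses, gives 72%. There is no reserve for dropout.

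These figures assume an SD of 60 s for the quantity analysed, equal groups and no baseline adjustment. That the stated figure is wrong does not depend on which test is chosen; that a factor of 2 was dropped is the likely explanation, not an established one. A statistical analysis plan held elsewhere would not resolve this, because the protocol itself states both the inputs and the incorrect result. It needs correcting.

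**What to change.** Keep 20 participants and replace the power statement in the Sample Size Calculation section with wording such as:

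*With 10 participants per group, an SD of 60 s and a two-sided alpha of 0.05, power to detect a 60 s difference is 56% (46% if 8 per group complete). The difference detectable with 80% power is 79 s (90 s if 8 per group complete).*

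Remove the claims that 8 per group provides 80% power and that 10 leaves a reserve for losses. In the same edit, say what the 60 s SD describes (final times, changes or residuals), since the new figures depend on it.

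If higher power is to be claimed, base it on a specified baseline-adjusted analysis and state the residual SD and its source. About 45 s or less is needed for 80% power at 10 per group with two-sided testing.

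The cost is protocol wording and a less favourable stated power. No extra participants, visits or procedures are needed. Re-running EPIDAT with the stated inputs would confirm the correction.

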### **Strategy for Recruiting Participants**

The recruitment strategy will utilize the researchers' social media accounts (Instagram and Facebook) to reach recreational runners who meet the inclusion criteria for this study. Following this, an Excel database will be created with the participants' key information to ensure data traceability. Communication with the runners will be handled via WhatsApp and email.

### **Study Development Locations**

The study will take place at Saldarriaga Park (Chía), which has a jogging track with a certified distance of 520 meters, and the athletic track at San Bartolomé La Merced School, with a certified distance of 330 meters in the inner lane and 370 meters in the outer lane. These locations were chosen to replicate the real conditions of a road race, as well as for their proximity and convenience for the research participants.

### **Bias Control**

The following actions will be taken to control bias:

##### **a. Generation of the randomization sequence**

The randomization method used will be block randomization (Ledesma, J. & Balaguer, J. 2021). The randomization sequence will be generated using a clinical trial randomization generator developed by José María Montiel Company of the University of Valencia to

distribute the 20 athletes into two groups: polarized (POL) and threshold (THR). This task will be performed by personnel external to the research group.

**b. Concealment**

The concealment of the randomization sequence will be carried out using opaque envelopes, sealed and numbered sequentially from 1 to 20. This process will be performed by an individual external to the research group.

